### *3.5.2 Physical and Neurological Examinations*

All physical and neurological examination results will be presented in data listings.

### *3.5.3 Clinical Laboratory Assessments*

Safety laboratory evaluations obtained from the following clinical laboratory tests will be collected:

- Hematology – complete blood count, including: reticulocytes (%), hematocrit, hemoglobin, platelet count, red blood cell (RBC) count, white blood cell (WBC) count, WBC with differential, including percentage and absolute measures for neutrophils, lymphocytes, monocytes, eosinophils and basophils.
- Chemistry – alanine aminotransferase, albumin, alkaline phosphatase, aspartate aminotransferase, bicarbonate, blood urea nitrogen, calcium, chloride, cholesterol, creatine phosphokinase, creatinine, cystatin C, gamma-glutamyl transferase, glucose, glutamate dehydrogenase, lactate dehydrogenase, magnesium phosphorus, potassium, sodium, total bilirubin, direct bilirubin, indirect bilirubin, total protein, triglycerides and uric acid.
- Coagulation – prothrombin time (partial) and thromboplastin time.
- Urinalysis – bilirubin, color and appearance, glucose, ketones, leukocytes, RBC, WBC, nitrite, occult blood, pH, protein, specific gravity and urobilinogen.

Results of all evaluations (normal, abnormal clinically significant, abnormal not clinically significant, not done) from each laboratory test will be tabulated by study visit. Descriptive statistics will be provided using the International System of Units (SI units), including absolute and percentage CFB. Both scheduled and unscheduled post-BL values will be included. Unscheduled visits will be summarized as one summary assessment at the end of all scheduled study visit summaries.

A listing of all laboratory evaluations and abnormal clinically significant laboratory evaluations will also be provided. Laboratory values outside the normal ranges will be flagged in the data listings.

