8.2.3. Clinical Safety Laboratory Assessments

Refer to [Appendix B](#) for the list of clinical laboratory tests to be performed.

The Investigator must review the laboratory report, document this review, and record any clinically significant changes occurring during the study as an AE. The laboratory reports must be filed with the source documents.

Abnormal laboratory findings associated with the underlying disease are not considered clinically significant unless judged by the Investigator to be more severe than expected for the participant's condition.

All laboratory tests with values considered clinically significantly abnormal during participation in the study should be repeated until the values return to normal or baseline or are no longer considered clinically significant by the Investigator or Medical Monitor.

If clinically significant values do not return to normal/baseline within a period of time judged reasonable by the Investigator, the etiology should be identified, and the Sponsor notified.

All protocol-required laboratory tests, as defined in [Appendix B](#), must be conducted in accordance with the laboratory manual and the SoA ([Table 1](#)).

If laboratory values from non-protocol specified laboratory tests performed at the institution's local laboratory require a change in participant management or are considered clinically

significant by the Investigator (e.g., SAE or AE or dose modification), then the results must be recorded.

8.2.4. *Electrocardiograms*

Triplet 12-lead ECG will be obtained using an ECG machine that automatically calculates the heart rate and measures PR, QRS, QT, and QTc intervals. All ECGs should be performed after the participant has rested quietly for at least 10 minutes in a supine position.

At each time point at which triplet ECG are required, 3 individual ECG tracings should be obtained as closely as possible in succession, but no more than 2 minutes apart.

8.2.5. *Echocardiograms*

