### 2.2 Study Objectives and Endpoints

Primary Objective	Primary Endpoints

To assess the safety and tolerability of EDG-5506 in adults with BMD

	

Incidence, frequency and severity of adverse events (AEs), and serious adverse events (SAEs) in participants treated with EDG-5506

Secondary Objectives	Secondary Endpoints

To assess the change in individual safety parameters

	

Incidence of treatment-emergent (TE) abnormal laboratory test results (clinical chemistry, hematology, coagulation and urinalysis)

Change from baseline (CFB) in:

Safety laboratory parameters

Vital signs

Physical and neurological examinations

Cardiac function, as assessed by electrocardiogram (ECG) parameters

Cardiac function, as assessed by an echocardiogram

Pulmonary function, as assessed

	

by forced expiratory volume in one second (FEV1) and forced vital capacity (FVC)

○ Columbia Suicide Severity Rating Scale (C-SSRS)

• To assess the PK profile of EDG-5506 in adults with BMD

	

• PK concentration levels of EDG-5506

Tertiary/Exploratory Objectives	Tertiary/Exploratory Endpoints

• To investigate the effects of EDG-5506 on biomarkers of muscle fiber damage in adults with BMD

	

• CFB in biomarker measures as assessed by:

○ Serum creatine kinase (CK)

○ Serum cardiac troponin I

○ Serum myoglobin

○ Serum cardiac troponin T

○ Serum N-terminal prohormone brain natriuretic peptide (NT-proBNP)

○ Plasma troponin I tissue-specific isoforms (fast-skeletal, slow-skeletal)

○ Plasma Somascan® proteomics

• To assess the effects of EDG-5506 on functional measures in adults with BMD

	

• CFB in functional assessments, as measured by:

○ NSAA

○ NSAD

○ 4-stair climb

○ 100-meter timed test

○ Muscle strength testing

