### 3.1.5 Summary Statistics

Categorical data will generally be summarized with counts and percentages of patients. The denominator used for the percentage calculation will be clearly defined. Continuous data will generally be summarized with descriptive statistics including n (number of non-missing values), mean, median, standard deviation, minimum, and maximum.

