#### 3.5.1.2 AE Summaries

A patient who reported multiple AEs that map to a common PT or SOC is counted only once for that PT or SOC at the highest severity reported and at the greatest relationship to study drug. The number and percentage of subjects who experienced at least one AE will be tabulated by SOC and PT with respect to dose level/treatment group for each study part. The same tabulation will also be applied to any SAE, any AE leading to premature discontinuation from the study, TEAEs and treatment-emergent SAEs.

The number and percentage of patients who experienced at least one AE will also be tabulated by SOC and PT within each dose level/treatment group with respect to relationship to study drug (related, not related) and severity (mild, moderate, severe).

Patient listings will also be provided for all AEs, all SAEs, all AEs leading to early discontinuation from the study and all AEs leading to study drug interruptions. Length of interruptions will also be provided.

An overview of AEs will be provided including counts and percentages of patients with the following:

- Any TEAEs (overall and by maximum severity)
- Any study drug-related TEAEs
- Any serious AEs (SAEs)
- Any TEAEs leading to discontinuation of study drug
- Any TEAEs leading to discontinuation of study

- Any AEs leading to death.

Separate tables including counts and percentages of patients will also be presented by system organ class and preferred term for each of the categories in the overview.

If an AE has incomplete start or stop dates, dates will be imputed to determine whether the AE was treatment-emergent. Details on the imputation for incomplete dates will be provided in the final SAP to correspond to CRF design and instructions.

Patient listings of all AEs will be presented, as well as listings specifically for SAEs and TEAEs leading to discontinuation of study drug.

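### No planned table gives the participant-level incidence of treatment-emergent laboratory abnormalities, and the pooled unscheduled row has no rule for repeat results from one participant

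*SAP*

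**What the plan says.** The endpoint. SAP 2.2 lists as a secondary endpoint "Incidence of treatment-emergent (TE) abnormal laboratory test results", covering chemistry, hematology, coagulation and urinalysis. Protocol Section 3 (Table 2) lists the same endpoint.

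The analysis. SAP 3.5.3 sorts each result into normal, abnormal clinically significant, abnormal not clinically significant or not done, and these results "from each laboratory test will be tabulated by study visit". Descriptive statistics with absolute and percentage change from baseline are added. On unscheduled results it says "Both scheduled and unscheduled post-BL values will be included" and then "Unscheduled visits will be summarized as one summary assessment at the end of all scheduled study visit summaries". Listings show all results, with out-of-range values flagged.

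What generates unscheduled results. Protocol 8.2.3 says that tests with clinically significant abnormal values "should be repeated until the values return to normal or baseline", or until they are no longer judged clinically significant.

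General rules. SAP 3.1.5 says "Categorical data will generally be summarized with counts and percentages of patients" and "The denominator used for the percentage calculation will be clearly defined". For continuous data the same section defines n as the count of non-missing values.

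Rules for other safety data. For adverse events, SAP 3.5.1.2 says that a patient with several events under one term "is counted only once for that PT or SOC". For ECGs, SAP 3.5.5 uses the minimum, maximum, last and worst post-baseline values, including unscheduled ones, and gives the number and percentage of subjects in each QTc category.

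**The concern.** An incidence needs three things: a definition of a case, a rule that counts each participant once, and a denominator. SAP 3.5.3 gives none of them for laboratory results. Treatment emergence is defined only for adverse events (SAP 3.1.8). Protocol 9.4.2 lists only change from baseline for laboratory parameters, and SAP Appendix A lists four panel summaries and no incidence table.

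The comparison with baseline matters here. Protocol Section 7 notes that ALT and AST are elevated in BMD itself, so a by-visit percentage of abnormal results mixes the disease with what emerged on treatment.

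The unscheduled row raises a second difficulty. It combines results from a study of up to 24 months and four dose periods. Under the retest rule, one participant with a persistent abnormality can contribute many of those results. The SAP does not say which of them are used or what they are divided by.

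At stake is whether the study report can state a named secondary safety endpoint from a pre-specified table, in a trial whose primary objective is safety.

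**Working it through.** Neither document states a laboratory incidence or a formula, so there is no plan figure to reproduce. The check is direct counting.

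**Inputs**
- N = 8: the approximate target of evaluable participants (Protocol 9.2, SAP 2.5), used here as the number in the SAF.
- Scheduled post-baseline chemistry and hematology visits: 9 in the first part of Protocol Table 1 and 4 in the second, so 9 + 4 = 13. The table was extracted from PDF and its columns may be misaligned, but the result below needs only 8 visits.
- Numbers of retests and of abnormal participants: assumptions for illustration. The documents give none.

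**1. Can the by-visit table give the incidence?** Suppose that it shows 1 of 8 abnormal at each of the 13 visits.
- The same participant every time: ever-abnormal incidence = 1/8 = 12.5%.
- Different participants, with all 8 affected at least once over the 13 visits: 8/8 = 100%.
- The same participant every time, already abnormal at baseline and never worse: treatment-emergent incidence = 0/8 = 0%.

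The by-visit rows look the same in all three cases. Panels sampled at fewer than 8 post-baseline visits have a lower ceiling, but the ambiguity is the same.

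**2. What can the unscheduled row show?** Suppose that one participant has 5 abnormal retests and one other participant has a single normal unscheduled test.

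| Counting rule | Calculation | Abnormal |
|---|---|---|
| Records | 5/(5 + 1) | 83.3% |
| Participants in the row | 1/2 | 50% |
| All participants, each at the worst value | 1/8 | 12.5% |

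Two things change between the first and last lines. Counting participants instead of records takes 83.3% to 50%. Changing the denominator from those retested to all participants takes 50% to 12.5%. Only the first step is due to repeat counting. If the retested participant's final normal result is also in the row, the record figure is 5/(5 + 1 + 1) = 71.4%.

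**3. Sensitivity to the number of retests.** Suppose instead that only one participant is retested, with k abnormal results and then one normal.
- By record, k/(k + 1): k = 1 gives 1/2 = 50%, k = 3 gives 3/4 = 75%, and k = 6 gives 6/7 = 85.7%.
- Records divided by 8, k/8: 12.5%, 37.5% and 75%.
- Participants over all 8, at the worst value: 1/8 = 12.5% for every k.

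The row therefore depends on a counting rule that the SAP does not state.

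**4. Continuous statistics.** Because SAP 3.1.5 defines n as non-missing values, the natural reading is that each retest enters the mean, SD and change from baseline in the unscheduled row as a separate observation. No selection rule says otherwise.

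**The case against.** A reader might infer that the SAP counts every retest as a separate case, and that pooling unscheduled visits is why the incidence is not estimated. The documents support neither.

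- SAP 3.5.3 does not state the unit in the unscheduled row. SAP 3.1.5 points to patients for categorical data, though only as a general practice, and promises a denominator. SAP Section 6 places table shells and programming specifications in separate documents, which may settle it.
- The incidence would be missing even with no unscheduled visits, because results are tabulated by visit with no definition of treatment emergence and no ever-abnormal summary.
- The by-visit rows are not biased downward. They describe status at each visit and do not claim to be cumulative.
- How many unscheduled tests there will be, and from whom, is not documented. That one participant's retests could dominate the row is possible under the retest rule, not established.

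There is also a partial route through adverse events. Protocol 8.2.3 has clinically significant laboratory changes recorded as adverse events, and SAP 3.5.1.2 counts each patient once per term. That stands, but it covers only what the investigator judges clinically significant. Protocol 8.2.3 and Appendix C.1 also set aside disease-associated findings unless they are more severe than expected. The endpoint is wider: abnormal results.

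Finally, the study is descriptive and small, and participant counts could be made by hand from the listings. This lowers the stakes. It does not replace a pre-specified definition, since two analysts working from the listings could define a treatment-emergent abnormality differently.

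**Conclusion.** The point holds in two parts. First, the plan as written does not estimate the secondary endpoint of incidence of treatment-emergent laboratory abnormalities: no case definition, participant-level rule or table is given. Second, the pooled unscheduled row has no rule for multiple results from one participant.

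On size, with 8 participants a by-visit table showing 1/8 at every chemistry or hematology visit is compatible with anything from 12.5% to 100% ever abnormal. In the assumed example the unscheduled row could read 83.3% or 50%, against 12.5% of all participants. The retest counts are illustrative, and 8 is the target number, not the final SAF.

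The documents do not show that retests will be counted as cases, and the missing incidence does not result from pooling. The gap affects a secondary endpoint in a study with no hypothesis tests. It should be closed before the SAP is finalized, and it does not undermine the primary adverse event analysis.

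**What to change.** Add to SAP 3.5.3:
- **Definition.** A treatment-emergent laboratory abnormality is a post-baseline result that is abnormal when the baseline was normal, or a shift from abnormal not clinically significant at baseline to clinically significant.
- **Counting.** Count each participant once per parameter at the worst post-baseline value, using scheduled and unscheduled results. Where a test can be abnormal in both directions, count low and high separately.
- **Denominator.** Use SAF participants with a baseline and at least one post-baseline value for that parameter.
- **Reporting.** Give the number and percentage with any treatment-emergent abnormality and, separately, with a clinically significant one. The second alone would largely repeat the adverse event tables.

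Add this summary to Tables 14.3.4.1 to 14.3.4.4. Keep the by-visit summaries. Drop the pooled unscheduled row, or limit it to one stated value per participant, and leave all retests in the listings.

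The worst-value approach is already in the SAP for ECGs. The cost is SAP wording, changes to four table shells and a little more programming. No new data are needed.

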### *3.5.4 Vital Signs*

Vital signs include systolic blood pressure (mm Hg), diastolic blood pressure (mm Hg), pulse rate (bpm), respiratory rate (bpm), temperature (°C), height (cm), weight (kg), arm span (cm) and ulna length (cm) (arm spans and ulna length only if subject is unable to stand for a standing

height measurement). . Summary statistics for vital sign values and the CFB will be presented at each scheduled visit. A listing of vital signs will also be provided.

### 3.5.5 *Electrocardiograms (ECGs)*

For standard supine resting 12-lead ECG parameters, descriptive statistics will be provided for the ECG measurements at BL (PR, QRS, QT, QTcB, QTcF, RR) and CFB for the minimum post-BL value, maximum post-BL value, and last post-BL value. Both scheduled and unscheduled post-BL values will be considered for the summaries. Outlying QTcF and QTcB intervals will be determined using the criteria outlined below.

Absolute QTc interval prolongation categories include:

- QTc interval >450 msec,
- QTc interval >480 msec, or
- Any QTc interval >500 msec.

CFB measurement in QTc interval categories include:

- QTc interval increase >30 msec, or
- QTc interval increase >60 msec.

Number and percentage of subjects for each category above will be provided.

For interpretation of clinical significance (abnormal, indeterminate, normal, not evaluable/unknown), a frequency table will be presented at each post-dose assessment and for the worst value between post-dose assessments.

Summary statistics for electrocardiogram values and the CFB will be presented by treatment group at each scheduled visit. ECG results will be listed at each assessment.

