5.2. Exclusion Criteria

Participants are excluded from the study if any of the following criteria apply:

Medical Conditions

1. Any clinically significant changes during or following the completion of Study EDG-5506-001 that would affect the potential safety of the participant to receive EDG-5506.
2. Cardiac echocardiogram ejection fraction <45% or New York Heart Association (NYHA) Class III or Class IV.
3. Baseline 12-lead electrocardiogram (ECG) that demonstrates clinically relevant abnormalities that may affect participant safety or interpretation of study results.
4. Forced vital capacity (FVC) predicted <65% or using daytime (mechanical or noninvasive) ventilatory support.
5. Moderate or severe renal or hepatic impairment (eGFR <60 mL/min/1.73 m²).

6. Positive test for hepatitis C antibody (unless negative HCV PCR), hepatitis B surface antigen, or human immunodeficiency virus (HIV) antibody at screening.

Prior/Concomitant Therapy

7. History of substance abuse or dependency.
8. Receipt of oral corticosteroids for >5 days in the previous 6 months at a dose of >5 mg equivalent per day. Lower oral doses or inhaled/intranasal steroids are permitted.
9. Receiving moderate or strong cytochrome P450 CYP3A4 inhibitors or inducers.
10. Participation in any other investigational drug study or use of use of an investigational drug within 30 days or 5 half-lives (whichever is longer) of dosing in the present study.

Other Exclusions

11. Participants who are unlikely to comply with the study protocol or, in the opinion of the Investigator, would not be a suitable candidate for participation in the study.
12. Medical history or other medical or psychiatric condition including recent (within the past year) or active suicidal ideation/behavior or laboratory result or abnormality that may increase the risk of study participation or, in the Investigator's judgment, make the participant inappropriate for the study. Includes venous access that would be too difficult to facilitate repeated blood sampling.

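### The ECG interpretation table and the absolute QTc counts in SAP 3.5.5 do not separate abnormalities present at baseline from new ones (minor)

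*SAP*

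**What the plan says.** SAP 3.5.5 plans several ECG outputs. Two matter here.

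- **Overall interpretation.** The levels are given as "For interpretation of clinical significance (abnormal, indeterminate, normal, not evaluable/unknown"), and "a frequency table will be presented at each post-dose assessment and for the worst value between post-dose assessments". The table is confined to post-dose readings.
- **Absolute QTc limits.** Under "Absolute QTc interval prolongation categories include" the SAP lists values above 450, 480 and 500 msec. It then states that "Number and percentage of subjects for each category above will be provided". No condition on the baseline value is attached.

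The same section also plans outputs that do use baseline: QTc increases above 30 and 60 msec ("CFB measurement in QTc interval categories include"), change from baseline in the intervals for the minimum, maximum and last post-baseline value, and change from baseline at each scheduled visit. ECG results are listed at each assessment. On which readings count, it says "Both scheduled and unscheduled post-BL values will be considered for the summaries".

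On entry, Protocol 5.2 criterion 3 excludes a baseline ECG "that demonstrates clinically relevant abnormalities that may affect participant safety or interpretation of study results". It states no QTc limit.

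**The concern.** The study has no control arm, so a participant's own baseline is the only reference that can separate what the disease brought in from what arose on treatment. Protocol 2.2.1 describes BMD as a disease of cardiac as well as skeletal muscle, so an abnormal but non-relevant ECG at entry is plausible. If it persists, it will appear as abnormal at each post-dose visit and in the worst-value row, in a table that does not show it was there before the first dose. A participant who enters with QTc above 450 msec and stays there is counted beside one who crosses 450 msec on treatment.

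There is a smaller labelling problem. The interpretation table is introduced as one of clinical significance, but its single abnormal level does not separate significant from non-significant findings. The laboratory table in SAP 3.5.3 does: "Results of all evaluations (normal, abnormal clinically significant, abnormal not clinically significant, not done"). A participant who moves from a non-significant to a significant abnormality therefore stays in the same cell of the ECG table.

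What is at stake is how clearly two descriptive safety tables can be read. Change from baseline in ECG parameters is a secondary endpoint, and these tables sit beside it.

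**Working it through.** The plan gives no figure to reproduce: there is no hypothesis test, and the target of about 8 evaluable participants was set empirically (Protocol 9.1 and 9.2). The check is of what the tables can show.

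**1. Readings per participant.** In the Schedule of Activities (Protocol Table 1), the ECG is marked at Visit 1 (screening) and at Visits 6, 8, 10, 11, 13, 15, 17, 19, 23 and 27. Under SAP 3.1.3 the scheduled baseline is the screening ECG. That is one baseline against 10 scheduled post-dose readings, so a lasting baseline abnormality is counted at every visit and in the worst-value row.

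**2. Interpretation table.** Take N = 8 and two assumed cases.

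| Case | Abnormal at baseline | Abnormal at worst post-dose | SAP table | New among those not abnormal at baseline |
|---|---|---|---|---|
| A | 2 | the same 2 | 2/8 = 25.0% | 0/6 = 0% |
| B | 0 | 2 | 2/8 = 25.0% | 2/8 = 25.0% |

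The planned table is identical in A and B. A baseline-by-worst shift table tells them apart.

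**3. Absolute QTc counts.** Set the >450 msec count beside the >30 msec increase category.

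| Baseline to post-dose (msec) | Increase | Counted >450 | Counted increase >30 | Newly >450 |
|---|---|---|---|---|
| 455 to 455 | 0 | yes | no | no |
| 445 to 455 | 10 | yes | no | yes |
| 420 to 455 | 35 | yes | yes | yes |

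The change categories pick up the third row. They do not separate the first from the second, so a crossing of a limit by 30 msec or less looks the same as no change.

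**4. Size per participant.** One carried-in abnormality adds 1/N to the percentage: 1/8 = 12.5 points. The tables use the safety population, which may exceed the number evaluable; the share then falls in proportion.

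**5. Chance that it arises.** The documents give no baseline ECG data, so the prevalence p of a carried-in abnormality is an assumption. The chance of at least one among 8 is 1 − (1 − p)^8:

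- p = 5%: 1 − 0.95^8 = 34%
- p = 10%: 1 − 0.90^8 = 57%
- p = 20%: 1 − 0.80^8 = 83%
- p = 30%: 1 − 0.70^8 = 94%

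These show sensitivity to p. They are not estimates for this population.

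**The case against.** The strongest case against is that the rest of the plan already supplies the baseline reference.

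- The protocol endpoint is change from baseline in ECG parameters, summarised at each scheduled time point (Protocol 9.4.2), and SAP 3.5.5 delivers it. The two outputs at issue are additions.
- QTc increases above 30 and 60 msec are tabulated against baseline.
- Listing 16.2.8.3 gives the ECG results. With about 8 participants a reader can compare each post-dose reading with baseline by eye.
- Under Protocol Appendix C.1, an ECG abnormality that worsens from baseline, is judged clinically significant and is not due to disease progression is an AE. SAP 3.1.8 and 3.5.1.2 then carry it into the treatment-emergent tables.
- Exclusion 3 also covers abnormalities that could affect interpretation of results, which reduces what is carried in.
- Table shells are separate documents (SAP 6), so the final layout cannot be fully judged.

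All of this stands, and it rules out three stronger conclusions that a reader might draw. The first is that the categorical ECG tables ignore baseline altogether: the >30 and >60 msec categories do not. The second is that new abnormalities cannot be seen: the listings and AE reporting show them. The third is that the SAP reports carried-in findings as drug effects: it nowhere calls these counts treatment-emergent, and any misreading needs a participant who entered with an abnormality.

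What the objection leaves open is narrower. The interval summaries do not cover the categorical interpretation, the change categories miss crossings of 30 msec or less, and a listing is not a table. The laboratory section is no model for a shift either, since it states none; it supports only the labelling point.

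**Conclusion.** The point holds in a limited form. As SAP 3.5.5 is written, the interpretation table and the >450, >480 and >500 msec counts cannot distinguish pre-existing from new abnormalities, and entry criteria permit both an abnormal ECG judged not relevant and a QTc above 450 msec. Each carried-in case moves a table entry by 12.5 points if N is 8. How often this happens depends on a baseline prevalence that the documents do not give, and on the abnormality persisting.

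The priority is minor. The study is descriptive, the primary endpoint (AEs and SAEs) is untouched, the change-from-baseline endpoint for ECG parameters is analysed, and individual data are listed. The case for acting is that the gap can be closed with data already scheduled.

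**What to change.** In SAP 3.5.5:

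1. Add a shift table of baseline interpretation by worst post-baseline interpretation, using the levels the SAP already names (abnormal, indeterminate, normal, not evaluable/unknown). State the order used to choose the worst. Split abnormal into clinically significant and not clinically significant only if the CRF records that distinction, which the documents do not show.
2. Beside each existing count of QTc above 450, 480 and 500 msec, for QTcF and QTcB, add the number newly exceeding the limit. The denominator is participants at or below that limit at baseline. Keep the existing counts and the >30 and >60 msec categories.

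The cost is SAP wording and two table shells. The screening ECG is already scheduled and baseline is already defined in SAP 3.1.3, so no new data are needed. The change should be made before the SAP is finalised ahead of database lock.
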